The first group of four patients at this level (Series II) will receive 48 Gy to the target volume (tumor) in 3 fractions of 16 Gy per fraction. If acute toxicity is acceptable, then the next four patients will be escalated to 54 Gy in 3 fractions of 18 Gy. Finally if a dose limit has not been reached, the last group of four patients will be treated to 60 Gy in 3 fractions of 20 Gy each.

It is important to note that dose to the normal tissues surrounding the target has not been allowed to dose escalate. Tolerance levels selected for these normal organs (see Table I. and Appendix I., are consistent with RTOG standards and normal tissue limits approved for UHCMC Protocol Case 13807 associated with Prostate Cancer with Cyberknife or Linac based SBRT irradiation.

Table I. Dose Specifications for Normal Organs (and Appendix I.)

1. Bowel – No more than 1 cc can receive 8 Gy/fx for a total of 24 Gy in 3 to 4 fractions.
2. Cord – No more than 0.3 cc can receive 6.7 Gy/fx for a total of 20 Gy in 3 to 4 fractions.
3. Stomach - No more than 1.0 cc can receive 7.3 Gy/fx for a total of 22 Gy in 3 to 4 fractions.
4. Liver – No more than 2/3 of liver volume can receive 5.7 Gy/fx for a total of 17 Gy in 3 to 4 fractions. Additionally within that volume – 800 cc should not receive more than 5.0 Gy/fx for a total of 15 Gy in 3 to 4 fractions.
5. Contralateral Kidney- No more than 5 % of the volume can receive more than 4.7 Gy/fx for a total of 14 Gy in 3 to 4 fractions.

It is thought that superior Cyberknife or Linac based SBRT treatment plans and delivery for this current cohort may be achievable without any increase in normal tissue toxicity as defined above. If this is not the case for any of the 12 patients included in the new series of cohorts and where the treatment plan has been determined to fail, the patient target volume dose will be reduced to the previous cohort dose. In no case will a dose escalation occur if the normal tissue toxicities criteria are not met in the treatment plan.

If 3 successive patients fail to meet the treatment planning criteria, the dose escalation study effort will be terminated and successive remaining patients will be treated at target dose from the previous cohort of 4 patients.

For this second series of the study, patients who fail by evidence of tumor regrowth or metastatic dissemination will not be retreated to the current dose level. However, if the subject experiences

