recurrence or progression, they will either be followed by observance; or if they require retreatment, they will be taken off study.

Radiation Toxicity:

All patients should be seen at 1, 3 and 6 months \pm 2 weeks, and then every 6 months by either the radiation oncologist or the urologist to evaluate radiation toxicities, or arranged to be seen locally if unable to return to Cleveland Medical Center with reports sent back for review. At 6 months post SBRT, the patient will be scheduled to be seen in Urology to evaluate their response to the therapy with imaging and an optional biopsy. Urinary and bowel irritation manifested as urgency, frequency, dysuria, infection and incontinence will be recorded. Medications to treat radiation side-effects will be recorded as well as dose and frequency. Acute Radiation Toxicity (<180 days from treatment date) will be documented using NCI common toxicity criteria, version 4.0. A shorter period of toxicity assessment for the purposes of dose escalation will be used. This will be done at the 1, 3 and 6 month follow-up visits after radiation therapy. More delayed short-term toxicities would be used in the final determination of the recommended Phase II dose.

Dose limiting Toxicity:

Acute Radiation Toxicity \geq grade 3 in the Gastrointestinal and renal/genitourinary categories of the common terminology criteria for adverse events 4.0 (CTCAE) will be considered dose limiting (see above). The maximum tolerated dose will be one dose level below which the adverse event, as described above, occurred (See statistical section).

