7.0 PATIENT ASSESSMENTS

Follow-up schedule and parameters assessed will be as follows:

		Treatment			Months Post-RT							
Parameters	Screening	Dose 1	Dose 2	Dose 3	1	3	6	12	18	24	30	36
History & Physical	X				X	X	X	X	X	X	X	X
Pregnancy Test	X											
Toxicity Evaluation					X	X	X	X	X	X	X	X
Biopsy	X						X ²					
MRI or CT of chest and Abdomen	X						X	X	X	X	X	X
Radiotherapy		X	X	X								
ELISA Blood Draws ¹		X ¹	X ¹	X ¹								

¹ To be drawn within 2 hours prior to and following completion of fractionated radiation therapy

² Patient will be given the option to have this procedure between 6 to 12 months follow up post RT. Standard stains with H & E as well as any staining to assess tissue viability will be ordered as available to possibly include NADH

(marker of metabolism) and MIB-1 (proliferation marker) or propidium iodide, which is a marker of cell membrane integrity and thus, death.

Post-Treatment Follow-up Schedule

After radio-surgery, follow-up will be done at 1, 3 and 6 months and then every 6 months post radiosurgery for a total of 36 months.

If viable tumor is identified or enhancement on any post therapy follow-up CT or MRI is identified, the patient may be offered additional treatment or observation, based on imaging analysis or patient preference and co-morbid illness clinical status. If the patient receives any re-treatment, they will be taken off study.

Radiation treatments for this subject will cease if any DLT's occur. The patient will then be followed every 6 months until 36 months after the radiation treatment.

Between 6 to 12 months following the end of RT, an optional percutaneous renal biopsy of the target tumor under US or CT guidance will be offered.

Acute vs. Late Toxicity

Acute toxicity monitoring: Acute side effects (\leq 180 days from RT start) will be documented using the using the NCI Common Toxicity Criteria version 4.0. (CTCAE)

Late toxicity monitoring: All late ($>$ 180 days from RT start) side effects will be evaluated and graded according to the. NCI Common Toxicity Criteria version 4.0. (CTCAE)

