9.0 STATISTICS

Statistical Considerations

The primary goal of this study is to compare and evaluate toxicities across four varied treatment schemes using a dose escalation design with four cohorts of 4-8 patients each. Escalation to the next dose will take place if no DLT's are observed in the first four patients treated at the current dose. If 2 or more DLT's are observed in the first four patients, then escalation is stopped. If 1 DLT is observed, then four more patients are treated at the same dose, and dose escalation stops if 2 or more of these next four (3/8 of patients treated at that dose) experience a DLT. If the probability of a DLT is 40%, there is a 71% chance of stopping at the current dose, whereas if the probability of DLT is 10%, there is only a 7% chance of stopping the dose escalation.

All analyses of the data will be descriptive. Clinical and radiographic efficacy will be summarized by calculating Kaplan-Meier curves for the following: overall survival, disease-free

survival, time to local progression, time to distant failure. Data from all dose groups will be pooled in these analyses. Survival rates estimated from the Kaplan-Meier curves will be estimated with 95% confidence intervals. Rates of acute and late side effects and adverse events will be summarized as proportions, with 95% confidence intervals.

Sample Size

The number of patients studied in this trial is determined by the dose escalation strategy and the number of DLT's that are observed at each dose level. With four dose levels and cohorts of 4-8 subjects per dose, the minimum sample size is 2 and the maximum is 32. It is expected that around 20 subjects will be enrolled. This design with cohort sizes of 4-8 per dose ensures that the probability of escalating to the next dose is .93 when the probability of DLT is .1, but is only .05 when the probability of a DLT is .6.

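### Severe GI or renal/GU events after day 180 enter no escalation or MTD count, and the window that defines a countable event is stated inconsistently

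*Combined protocol and SAP*

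**What the plan says.** Under Dose limiting Toxicity, section 6.0 counts acute toxicity of grade 3 or higher in the gastrointestinal and "renal/genitourinary categories of the common terminology criteria for adverse events 4.0 (CTCAE) will be considered dose limiting (see above"). The MTD follows from that event: "The maximum tolerated dose will be one dose level below which the adverse event, as described above, occurred".

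Escalation uses the same count. Section 9.0 says "Escalation to the next dose will take place if no DLT's are observed in the first four patients treated at the current dose". Section 6.0 (Series I) and section 9.0 stop at 2 or more of 4, or 3 or more of 8. In Series II the first step is "If acute toxicity is acceptable, then the next four patients will be escalated to 54 Gy in 3 fractions of 18 Gy".

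The window is described in several places:

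- Section 6.0, Radiation Toxicity: "Acute Radiation Toxicity (<180 days from treatment date) will be documented using NCI common toxicity criteria, version 4.0".
- The same paragraph announces a shorter assessment period for escalation without giving its length, and continues "This will be done at the 1, 3 and 6 month follow-up visits after radiation therapy". Those visits carry a 2-week allowance either way.
- Section 7.0 counts acute effects up to and including 180 days from the start of radiotherapy. Late effects are those beyond "180 days from RT start) side effects will be evaluated and graded according to the" CTCAE. The visit schedule in section 7.0 is headed in months after radiotherapy.

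Three provisions could bring later toxicity into play. The opening condition for Series II asks whether normal-tissue toxicity has been a problem, with no restriction to acute events. Section 6.0 adds "More delayed short-term toxicities would be used in the final determination of the recommended Phase II dose". Section 12.0 allows a pause for an unanticipated adverse event that poses unreasonable risk. None states a number of events.

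**The concern.** The primary objective in section 2.0 is safety, and toxicity is evaluated at every visit to month 36. The later part of that information has no defined route into the dose decision. Section 9.0 only summarizes late effects as proportions with confidence intervals.

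Suppose two of four patients at 32 Gy have a grade 3 bowel event. Dated before day 180, these events stop the trial and put the MTD below 32 Gy. Found at the 12-month visit, they leave the rule pointing to the next dose and the MTD where it was. New patients could then be sent above a dose that has already produced the event count the plan treats as unacceptable. The tabled stopping probabilities protect patients only to the extent that severe toxicity appears before day 180.

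Separately, a 6-month visit can fall on either side of day 180, so the classification of an event that begins around then depends on which sentence of the protocol is applied.

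**Working it through.** **1. The plan's own table.** With acute DLT risk p, a level stops at 2 or more of 4, or at 1 of 4 followed by 2 or more of the next 4:

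Pr(stop) = T + 4p(1−p)³·T, where T = Pr(2 or more of 4).

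At p = 0.10, T = 0.0523 and Pr(stop) = 0.0523 + 0.2916 × 0.0523 = 0.068. At p = 0.20 it is 0.255, and at p = 0.40 it is 0.706. The table in section 6.0 gives 0.07, 0.25 and 0.71. The table therefore reproduces from the DLT count alone and contains no late-event term. At p = 0.05, which is not tabled, the result is 0.016.

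**2. Adding late events to the same boundary.** The documents give no late rate, so total and acute risks are assumed. Late risk in a patient without an acute event is L = (total − acute)/(1 − acute). After the acute rule has been passed, the level closes if acute plus late events reach 2 of 4 or 3 of 8.

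For 40% total and 10% acute risk, L = 0.30/0.90 = 1/3. The parts are:

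- acute rule stops: 0.0676
- 0 of 4 acute (0.6561), then 2 or more of 4 late (0.4074): 0.2673
- 1 of 4 then 0 of 4 acute (0.1913), then 2 or more of 7 late (0.7366): 0.1409
- 1 of 4 then 1 of 4 acute (0.0850), then 1 or more of 6 late (0.9122): 0.0776

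The sum is about 0.553. If only half the late risk has appeared at the check, L becomes 1/6 and the sum is 0.274. Other cases by the same formula:

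| Total risk | Acute risk | Stated rule stops | Look-back, half of late risk seen | Look-back, late follow-up complete |
|---|---|---|---|---|
| 40% | 20% | 0.255 | 0.416 | 0.593 |
| 40% | 10% | 0.068 | 0.274 | 0.553 |
| 40% | 5% | 0.016 | 0.218 | 0.538 |
| 30% | 10% | 0.068 | 0.186 | 0.368 |
| 20% | 5% | 0.016 | 0.069 | 0.176 |
| 10% | 5% | 0.016 | 0.026 | 0.044 |

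**3. When late data could still affect escalation.** There are seven levels (24, 32, 40 and 48 Gy in 4 fractions; 48, 54 and 60 Gy in 3) and six escalation decisions. Assume a wait of w months per level and ignore accrual time, which would add decisions after the late data. Level k has its 12-month visit at (k−1)w + 12, and decision j falls at jw. The numbers of decisions at or after that visit, from the lowest level to the highest, are:

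- w = 6: 5, 4, 3, 2, 1, 0, 0
- w = 3: 3, 2, 1, 0, 0, 0, 0
- w = 1: none at any level

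**4. The 6-month visit and day 180.** Take 6 months as 183 days and assume fractions on consecutive days, so that radiotherapy ends 0 to 3 days after it starts. The visit window, counted from the start, runs from days 169–197 to days 172–200. Of the 29 allowed days, 17 to 20 (59% to 69%) lie after day 180. These are visit days, not events. An event with onset before day 180 is acute whenever it is recorded, so the affected onsets run from day 180 to about day 200. A course lasting 10 days would move the end to about day 207. Day 180 itself is acute in section 7.0 but not in section 6.0.

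**The case against.** The strongest reply is that the split looks deliberate. Section 6.0 wants a short period for escalation and leaves more delayed toxicity to the recommended Phase II dose. It also holds normal-tissue dose to fixed limits for bowel, stomach, liver, cord and the other kidney, and bars escalation when a treatment plan fails them. Section 12.0 records events of grade 2 and above and sends serious ones to the safety committee and the IRB. A late severe event would be seen, and people could act on it.

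Much of this stands. A reader might infer that late toxicity is ignored, or that a late event can never halt the trial. The documents do not support either: the Series II condition, the recommended-dose sentence and the section 12.0 pause all leave room to act. What they lack is a count, a threshold or a stated time limit. The recommended-dose sentence does not say whether toxicity after day 180 qualifies as short-term. The normal-tissue limits constrain the plan before treatment and do not respond to observed toxicity. Table I also sets no limit for the treated kidney or the ureter.

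A reader might also infer from the 59% to 69% figure that most toxicity found at six months would escape the DLT count. It would not, because the figure counts permitted visit days and earlier onsets still qualify. If the unspecified shorter period ends before day 180, the day-180 cut would not even govern escalation. That part is an unclear definition, to be cured by wording.

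The complete-follow-up probabilities are upper bounds, since escalation would not wait for late data. The look-back also leaves one gap: a single late event in four patients does not trigger four more, as one acute event would.

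**Conclusion.** The point holds on the counting rules. Severe GI and renal/GU events after day 180 enter neither the escalation count nor the MTD, although the trial collects them to month 36.

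The size depends on risks the documents do not give. If most severe toxicity is acute, little changes. If 40% of patients have a severe event and 10% have it acutely, the rule stops with probability 7%. The look-back closes the level with probability 27% to 55%, depending on how much late risk has appeared. At 10% total and 5% acute risk, closing rises only from 2% to 4%.

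The effect on escalation is concentrated at the lower levels and longer waits. At the upper levels, or with short waits, the gain is to the MTD and the dose recommendation. The window inconsistency is a smaller, separate matter. The change should be made; confidence is medium because the acute/late split is assumed.

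**What to change.** 1. Sections 6.0 and 7.0: state one clock and one DLT window that includes the 6-month visit with its 2-week allowance. Say whether escalation waits for that visit, and define or delete the shorter period.
2. Sections 6.0 and 9.0: before each escalation, and before naming the MTD, count all GI and renal/GU events of grade 3 or higher so far, acute and late, at each earlier level against 2 of 4 or 3 of 8. If a level crosses the boundary, enrol no one at that level or higher and place the MTD below it. Escalation does not wait for late follow-up. State also what happens to a patient already mid-course at a higher level.
3. Section 6.0: replace the open reference to more delayed toxicity with the same count, taken after the 12-month visit at the dose to be recommended for Phase II.

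No new visits or data are needed. The recommended dose is named about 6 months later (month 12 instead of month 6 at that dose), within the planned 36 months. If the 6-month visit is awaited, each level may take up to about 3 weeks longer (day 200 against day 180). The check is weakest at the highest doses, which have the least late follow-up.

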7.0 PATIENT ASSESSMENTS

Follow-up schedule and parameters assessed will be as follows:

		Treatment			Months Post-RT							
Parameters	Screening	Dose 1	Dose 2	Dose 3	1	3	6	12	18	24	30	36
History & Physical	X				X	X	X	X	X	X	X	X
Pregnancy Test	X											
Toxicity Evaluation					X	X	X	X	X	X	X	X
Biopsy	X						X ²					
MRI or CT of chest and Abdomen	X						X	X	X	X	X	X
Radiotherapy		X	X	X								
ELISA Blood Draws ¹		X ¹	X ¹	X ¹								

¹ To be drawn within 2 hours prior to and following completion of fractionated radiation therapy

² Patient will be given the option to have this procedure between 6 to 12 months follow up post RT. Standard stains with H & E as well as any staining to assess tissue viability will be ordered as available to possibly include NADH

(marker of metabolism) and MIB-1 (proliferation marker) or propidium iodide, which is a marker of cell membrane integrity and thus, death.

Post-Treatment Follow-up Schedule

After radio-surgery, follow-up will be done at 1, 3 and 6 months and then every 6 months post radiosurgery for a total of 36 months.

If viable tumor is identified or enhancement on any post therapy follow-up CT or MRI is identified, the patient may be offered additional treatment or observation, based on imaging analysis or patient preference and co-morbid illness clinical status. If the patient receives any re-treatment, they will be taken off study.

Radiation treatments for this subject will cease if any DLT's occur. The patient will then be followed every 6 months until 36 months after the radiation treatment.

Between 6 to 12 months following the end of RT, an optional percutaneous renal biopsy of the target tumor under US or CT guidance will be offered.

Acute vs. Late Toxicity

Acute toxicity monitoring: Acute side effects (\leq 180 days from RT start) will be documented using the using the NCI Common Toxicity Criteria version 4.0. (CTCAE)

Late toxicity monitoring: All late ($>$ 180 days from RT start) side effects will be evaluated and graded according to the. NCI Common Toxicity Criteria version 4.0. (CTCAE)

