Twenty patients who are not surgical candidates will be offered treatment with a radio-surgical technique. Four patients will be registered in each dose group. Treatments will be initiated with 4 patients utilizing the minimum dose and observe what happens. If no DLTs are observed, then escalation to the next set of 4 patients to the next initial dose level will occur. If 1 DLT is observed, treatment of the next set of 4 patients at the same dose level will occur. If zero or 1 additional DLTs are observed, then dose escalation occurs as previously described. However, if $\geq 2/4$ or $\geq 3/8$ are observed at a given dose level the trial stops. On average, this results in between 4-5 patients being treated before escalation. The table below shows the probability of stopping giving an underlying toxicity level using this design.

Table: Probability of stopping escalation given underlying toxicity

Underlying Pr(Toxicity)	0.1	0.2	0.25	0.3	0.35	0.4	0.5	0.6	0.7	0.8	0.9
Pr(Stopping)	0.07	0.25	0.37	0.49	0.61	0.71	0.86	0.95	0.99	0.998	0.999

If a patient fails original treatment, he or she will be either kept on study for observation, or if they require retreatment, they will be taken off study.

Series II

The next series will be reached if insufficient dose limiting toxicities have occurred upon completion of the initial dose escalation series I to a total dose of 48 Gy in 4 fractions to warrant limitation of further dose escalation.

At this level, if normal tissue toxicities for SBRT have not proven to be problematic for renal lesions, then “standard” dose and fractionations will be prescribed for subsequent patients as would be used for example in Lung cancer. Given the 90% expectant local control for lung

lesions given 20 Gy in 3 fractions, we are highly anticipating reaching an efficacious dose during series II of the trial. If the 12 Gy x 4 fraction cohort is irradiated without dose limiting toxicities, then 12 additional patients will be accrued for further dose escalation following dose toxicity criteria defined below:

Based on the Linear Quadratic Model commonly used for radiobiologic comparisons, each subsequent group of four participants will receive further dose escalation using a 3 fraction regimen to increase beyond 48 Gy in 4 fractions in 20% dose equivalent increments.

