Tumor measurements will be defined by the principal investigator or treating physician and confirmed by a radiation oncologist or radiologist not associated with this study. In addition, responses will be reported directly to the CCCC Data Safety and Toxicity Committee (DSTC) for confirmation of objective responses reported. Submissions will be made within accordance with reporting timelines. The study PI, co-investigators, and/or research staff will monitor all patients on the trial, and will evaluate patients at each treatment encounter and in follow-up. Serious adverse events are reported to the attending physician, the Principal investigator (PI), the DSTC, and the UHCMC IRB per IRB guidelines.

Accessing Electronic Medical Records

This study will access both paper and electronic medical records systems to obtain medical information for the subjects. Therefore, electronic medical records must be utilized to obtain medical information in a timely manner. The names will come from surgeon's offices (staff and records), tumor boards, surgical schedules, IDX and the surgeon's direct referral. Each patient will be approved by the surgeon before contact by the research individual occurs. Physician Portal, EMR and paper charts will be used to screen for eligibility. Paper copies of the eligibility criteria (pathology reports, laboratory results, etc.) will be kept in the shadow charts by the study coordinator. The shadow charts will be kept in a secure, locked area. Clinical data will be tracked in Oncore. Other data, such as treatment planning images, will be maintained on a password protected computer located in the Department of Radiation Oncology on a secured server.

Response Criteria

Response will be assessed using tumor measurements (longest dimension) obtained from MRI and/or CT with or without contrast, documentation of presence of metastatic disease, results of post-treatment pathology (if available).

Definitions of response:

- Stable – no change
- Progressive Disease – 20% or more increase in sum of diameters of the target lesion. The sum must also demonstrate an absolute increase of 5 mm or more or the presence of a new lesion or lesions.
- Partial Response - At least a 30% decrease in the sum of diameters of target lesions, taking as reference the baseline sum of diameters.
- Complete Response – no visible target lesions
- Pathological Complete Response – Based on increase or decrease of available biopsy results

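### Retreated patients leave the study with no stated further follow-up, and retreatment need not meet the progression definition, so local failures, later deaths, distant failures and late toxicity can go unrecorded

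*Combined protocol and SAP*

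**What the plan says.** The off-study rule appears three times, always triggered by retreatment.

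- Section 6.0, Series I, on a patient whose treatment fails: "he or she will be either kept on study for observation, or if they require retreatment, they will be taken off study".
- Section 6.0, Series II, on a patient with "recurrence or progression, they will either be followed by observance; or if they require retreatment, they will be taken off study".
- Section 7.0, Post-Treatment Follow-up Schedule: "If the patient receives any re-treatment, they will be taken off study".

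Section 7.0 also says what can lead to retreatment: "If viable tumor is identified or enhancement on any post therapy follow-up CT or MRI is identified", then "the patient may be offered additional treatment or observation, based on imaging analysis or patient preference and co-morbid illness clinical status". The same section keeps a patient with a DLT in six-monthly follow-up until 36 months. It has no matching sentence for retreated patients.

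Section 12.0, Response Criteria, holds the only definition of progression: "20% or more increase in sum of diameters of the target lesion", with an absolute increase of at least 5 mm, or a new lesion.

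Section 9.0 states: "Clinical and radiographic efficacy will be summarized by calculating Kaplan-Meier curves for the following: overall survival". The list goes on to disease-free survival, time to local progression and time to distant failure, pooled over dose groups. Acute and late side effects are reported as proportions with 95% confidence intervals. Section 9.0 gives no censoring rule, no event definition for disease-free survival or local progression, and no denominator for late toxicity.

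**The concern.** Two features of the plan combine badly.

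First, the trigger for retreatment is wider than the definition of progression. A patient retreated for enhancement or for viable tumour on biopsy, without the required growth or a new lesion, leaves with no event that the plan defines. With no later data, the natural handling is to censor that patient at removal as locally controlled.

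Second, removal is related to the course of the disease and to the patient's condition. Kaplan-Meier estimation needs censoring to be unrelated to later risk. Overall survival and time to distant failure run on past local failure, so they lose information from a selected group.

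Late toxicity belongs to the primary objective, safety. The first scheduled post-treatment scan is at month 6, and late toxicity starts after 180 days. A patient retreated on that scan contributes almost no late-toxicity observation.

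**Working it through.** **The plan's own figures.** The only calculated design figures are the stopping probabilities. With X and Y the DLT counts in the first and second four patients, P(stop) = P(X ≥ 2) + P(X = 1) × P(Y ≥ 2).

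- At a DLT probability of 0.10: 0.0523 + 0.2916 × 0.0523 = 0.068 (stated 0.07).
- At 0.40: 0.5248 + 0.3456 × 0.5248 = 0.706 (stated 0.71).

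They reproduce. They rest on acute DLTs, and the scheduled scans that could prompt retreatment begin only at month 6, as the acute window closes. The off-study rule does not change them. The plan gives no figure for censoring or loss to follow-up, so every input below is assumed.

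**Assumed inputs.** Exponential times over 36 months; local failure F = 7%, 20% or 30%; death without failure B = 20% or 40%; hazard ratio for death after failure (HR) 1, 2 or 4; share of failures retreated 50% or 100%. The 7% echoes the 93% control rate cited in Section 1.0, which had a mean follow-up of 12 months.

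**Overall survival.** Let a = −ln(1 − F), d = −ln(1 − B) and k = a + d − HR × d. With full follow-up,

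OS = exp(−a − d) + a × exp(−HR × d) × (1 − exp(−k)) / k, the last factor being 1 when k = 0.

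If every failure is retreated and censored on that date, Kaplan-Meier estimates 1 − B. For F = 20% and B = 20% (a = d = 0.2231):

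| HR | OS, full follow-up | OS, censored at retreatment | Difference |
|---|---|---|---|
| 1 | 0.64 + 0.16 = 80.0% | 80.0% | 0 |
| 2 | 0.64 + 0.2231 × 0.64 = 78.3% | 80.0% | +1.7 points |
| 4 | 0.64 + 0.1152 = 75.5% | 80.0% | +4.5 points |

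A simulation of 400,000 patients per scenario over the whole grid gave 0 points at HR 1, +0.3 to +4.1 at HR 2 and +0.7 to +9.3 at HR 4. The formula gives +9.2 for that last corner (F = 30%, B = 40%, all retreated).

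The sign can reverse. With HR 0.5 in the same example, OS with full follow-up is 0.64 + 0.8944 × (1 − 0.7155) / 1.5 = 81.0%, so censoring gives a figure 1.0 point too low.

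**Local progression.** If each failure is counted as an event before removal, the estimate is right: 93%, 80% and 70% are recovered. If a share u of failures is censored uncounted, the estimate becomes (1 − F)^(1 − u).

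| True 36-month control | u = 50% | u = 100% |
|---|---|---|
| 93% | 96% | 100% |
| 80% | 89% | 100% |
| 70% | 84% | 100% |

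The last column is a bound: it supposes that no failure met the Section 12.0 definition before retreatment. Disease-free survival behaves alike. With F = B = 20% it is 0.80 × 0.80 = 64% if failures are counted, 0.894 × 0.80 = 72% at u = 50%, and 80% at u = 100%.

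**Late toxicity.** If a share q of patients leaves at about month 6, stays in the denominator as event-free and would have had the same late-event rate as the rest, the reported proportion is (1 − q) times the true one. With 20% failing and 50% to 100% of them retreated, q is 10% to 20%, so the factor is 0.90 to 0.80.

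**Scale.** Section 9.0 expects around 20 patients, so each is 1/20 = 5% of the sample. With OS at 80% and no censoring, the 95% half-width is 1.96 × √(0.8 × 0.2 / 20) = 17.5 points.

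**The case against.** A reader might infer that everyone whose treatment fails is censored on failing, and that all the Kaplan-Meier results are therefore too favourable. The documents do not support that.

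- Failure alone removes nobody. Section 6.0 keeps observed failures in Series I on study and has the same split in Series II.
- A failure that meets Section 12.0 before removal is itself the event for local progression and disease-free survival. Once it is counted, later removal does no harm to those curves.
- Censoring is an inference. The plan neither defines off study nor states a censoring rule. Section 12.0 also lists post-treatment pathology among the inputs to response, so a positive biopsy might be treated as failure, although the progression definition does not say so.
- It is not established that retreated patients have the worst outlook. The choice depends partly on preference and comorbidity, and in poor surgical candidates the fitter ones may be retreated.
- Deaths without failure act the other way on local failure. If F = 20% and B = 40%, 1 − KM gives 20%, but cumulative incidence is 0.2231 / (0.2231 + 0.5108) × (1 − 0.48) = 15.8%. This overstates failure and is a separate matter.

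The efficacy analyses are also descriptive and secondary, with intervals wider than the survival shifts shown.

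All of this narrows the point. What remains is a rule stated three times, with no follow-up after it, and a trigger wider than the progression definition. Wide intervals do not correct a systematic loss, and late toxicity is part of the safety objective.

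**Conclusion.** The concern holds in limited form, and the change should be made. Followed as written, the plan can lose local failures in patients retreated without defined progression, and later deaths, distant failures and late toxicity in any retreated patient.

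The clearest effect is on local progression and disease-free survival. There the size depends on how many failures go uncounted: true control of 80% would read 89% if half were missed.

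For overall survival and distant failure, censoring would be informative, but direction and size depend on prognosis after retreatment. The survival shift ranges from none at HR 1 to about +9 points at HR 4, and it reverses if retreated patients do better. A general statement that the survival results are too favourable is not supported. No size was calculated for distant failure.

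Late-toxicity proportions are too low if removed patients remain in the denominator as event-free. Escalation decisions and stopping probabilities are not affected. All sizes rest on assumed inputs and on censoring at removal.

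**What to change.** 1. In Section 6.0 (Series I and Series II) and Section 7.0, replace the off-study wording with: *off protocol treatment; follow-up for survival, progression and late toxicity continues to month 36*. This changes data collection only, not who is retreated.
2. In Section 9.0, count retreatment of the target tumour as a local-failure event on its date, for time to local progression and for disease-free survival, unless progression was recorded earlier. State the censoring rule for each curve.
3. Report late toxicity with a stated denominator, and flag events that occur after retreatment.

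The cost is protocol and analysis wording plus continued data entry for a few patients. The local-control figure may be slightly less favourable, and some late toxicity will not be attributable to the first treatment alone.

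Separately, and optionally, report local and distant failure as cumulative incidence with death as a competing event, keeping Kaplan-Meier for overall survival.
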